5.2.2 Secondary endpoints

The secondary outcomes:

1. Time to insulin initiation and insulin dose required
2. Maternal morbidity at delivery (hypertensive disorders, antepartum and postpartum haemorrhage)
3. Mode of delivery
4. Gestational age at delivery
5. Postpartum glucose status, insulin resistance, and metabolic syndrome

EMERGE NUIG-2016-01, Statistical Analysis Plan Version 1, 21/03/2023

6. Postpartum BMI, gestational weight gain, and waist circumference
7. Infant birth weight
8. Infant size (large/small/appropriate for gestational age)
9. Neonatal height and head circumference at delivery
10. Neonatal morbidities (Need for neonatal care unit, respiratory distress, jaundice, congenital anomalies, Apgar score)
11. Neonatal hypoglycaemia (defined as plasma glucose <2.6mmol/L on one or more occasions starting 30-60 minutes after birth)
12. Cost effectiveness and budget impact of metformin treatment in addition to usual care
13. Treatment acceptability (Diabetes Treatment Satisfaction Questionnaire DTSQ and Rowan questionnaires)
14. Glycemic control, measured by participant glucocometer.

Quality of Life determined by EQ5D-5L questionnaire

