11.1 Subject Disposition

Different variables from the CRF will be considered to determine the number of patients who reached the various stages of the study. The following counts will be reported by study group:

- Number of participants randomised
- Number of randomised participants who received study medication at least once
- Number of participants who completed the study medication.
- Number of participants who had the delivery.
- Number of participants who completed the post-delivery follow-up visit.
- Number of participants who withdrew the study before completion.

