12.3 Baseline and Screening Conditions

Social history (smoking and alcohol), previous pregnancies, current pregnancy, vital signs, glucose tolerance test results, history of gastrointestinal events, lab test results, standard care (dietary and physical exercise advice) received, socioeconomic status and EQ5D-5L questionnaire responses will be summarised. Numerical values will be summarised using the mean, standard deviation, median, minimum and maximum, while categorical values will be summarized using counts and percentages.

A listing of all Diseases/Conditions will be provided for the analysis of the medical history. If possible, the most common conditions will be summarized using counts and percentages.

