14.1 Drug Exposure

The analysis of drug exposure will include summaries of the total dose received by treatment arm and visit (mean, Standard Deviation (SD), median, min and max). An exploratory analysis of how drug exposure may be related to changes in safety assessments will also be performed.

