14.2 Adverse Events

Some maternal events related to prenatal period, labour, delivery and the postnatal period are commonly experienced and are therefore exempt from safety reporting unless fatal, life threatening, medically important or results in persistent disability or incapacity (see Appendix for the list of exempted AEs). However, exempted AEs were recorded prior to protocol version 6.0 (dated 02 May 2019) and before the implementation of exemptions in safety reporting. The exempted AEs will be excluded in the analyses below.

The analysis of adverse events will include:

- A summary (by treatment arm) of the number of Adverse Events (AEs) reported (counts), and the number of participants experiencing any adverse event (counts and percentages) will be presented. Treatment arms will be compared using the chi-squared test.
- Summaries of each adverse event (coded as Preferred Term and System Organ Class) by treatment arm will be provided. Summaries will include number of events, number of participants (counts and percentages), severity and highest grade. Comparisons between treatment arms using chi-squared or Fisher's exact test (where enough information is available) will be presented. Note that the highest grade will be considered if a participant has different grades for the same adverse event.

EMERGE NUIG-2016-01, Statistical Analysis Plan Version 1, 21/03/2023

- Summaries of patients with AEs definitely, probably or possibly related to metformin, Insulin or interaction between metformin and Insulin, by preferred term and treatment arm will be given.

Separate table summaries will be presented for AEs occurring on the mother and for AEs occurring in the baby.

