14.3 Deaths, withdrawal, Serious Adverse Events and other Significant Adverse Events

Serious adverse events (SAEs) will be analysed in the same fashion as AEs. Withdrawals will be summarised as the number and percentage of patients who were withdrawn from the study by treatment arm.

14.3.1 *Withdrawal due to Adverse Events*

Withdrawals due to adverse events will be summarised as the number and percentage of patients who were withdrawn by treatment arm.

14.3.2 *Deaths*

In the unlikely case that deaths occur they will be summarised as the number and percentage of participants (mother or baby) who died within the study period by treatment arm.

14.3.3 *Other AE Assessments*

No other assessments or analyses are planned.

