14.7 ECGs

Not applicable.

15 Other Planned Analysis

No other analyses planned.

16 Reporting conventions

P-values ≥ 0.001 will be reported to 3 decimal places; p-values less than 0.001 will be reported as " <0.001 ". The mean, standard deviation, and any other statistics other than quantiles, will be reported to one decimal place greater than the original data. Quantiles, such as the median, or minimum and maximum will use the same number of decimal places as the original data. Estimated parameters, not on the same scale as raw observations (e.g., regression coefficients) will be reported to 3 significant figures.

17 **References**

- WHO. Diagnostic criteria and classification of hyperglycaemia first detected in pregnancy: a World Health Organization guideline. *Diabetes Res Clin Pract* 2014;103:341-63.
- ADA. American Diabetes Association Position statement: Gestational Diabetes Mellitus. *Diabetes Care*. 2004;27(Suppl 1):S88-S90.
- O Sullivan EP, Avalos G, O Reilly M, Dennedy C, Dunne F. ATLANTIC DIP: The prevalence and outcomes of gestational diabetes mellitus using new diagnostic criteria. *Diabetologia* 2011; 54(7):1670- 1675.

18 ***Listing of Tables, Listings and Figures***

Tables, listings and figures will be used to summarise the results of the analyses described in this SAP. Tables, listings and figures in the CSR will clearly display the title, endpoint(s) population, summary statistics calculated, type of analysis used, time points and any relevant footnotes.

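### Maternal GI symptoms and hypoglycaemia are exempted from AE reporting as study outcomes, but no SAP section explicitly assigns them to a by-arm summary on treatment

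*SAP*

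**What the plan says.** **Collection.** Protocol 8.3.2 schedules a GI symptom review and a hypoglycaemic-event review at prenatal visits about every two weeks. Figure 2 marks both at every prenatal visit from week 0 onwards.

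**Exemption.** Protocol 10.2 has a list of maternal events that are exempt from safety reporting because they are study outcomes held on the CRF. Three entries matter here:
- Item i, common pregnancy symptoms (nausea, heartburn, vomiting, flatulence, constipation): exempt unless they need hospitalisation.
- Item ii, GI side effects of metformin (nausea, vomiting, diarrhoea, flatulence): exempt unless they need hospitalisation or study drug is stopped.
- Maternal hypoglycaemia: exempt unless it needs hospitalisation.

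Events that are fatal, life threatening, medically important or disabling stay reportable. Figure 3 repeats this, and its footnote on stopping study drug is attached to the metformin row only.

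**Analysis.** SAP 14.2 sends the reader to an appendix ("see Appendix for the list of exempted AEs") and then says "The exempted AEs will be excluded in the analyses below". SAP 12.3 summarises "history of gastrointestinal events" at baseline. SAP 14.3.3 says "No other assessments or analyses are planned" and SAP 15 says "No other analyses planned".

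**The concern.** The protocol's reason for not reporting these events as AEs is that they are captured as outcomes. That reason holds only if the outcome data are then analysed, and the SAP does not explicitly provide for this.

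GI effects are the side effects the protocol expects from metformin. Section 17.2 calls them known and explains the titration by them, and section 9.1.2 has a procedure for participants who have them. The trial tests metformin in all women at diagnosis, including those who would be controlled by diet and exercise alone (about 60% according to protocol 6.1.5). For those women tolerability weighs heavily in the benefit-risk judgement.

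Maternal hypoglycaemia matters for a related reason. Protocol 6.1.6 links it to insulin, and protocol 6.2 gives its absence with metformin as an advantage. Insulin use may differ by arm, so this is a comparison the trial could make directly, yet no by-arm count is named.

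**Working it through.** The point concerns an analysis that is not specified, so the check is a trace from collection to reporting.

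**Step 1: what the AE tables can contain.** Under protocol version 6.0 a non-serious GI symptom or a hypoglycaemic event without admission need not be reported as an AE. The SAP appendix is not in the supplied text, so take both possibilities:
- *The appendix includes these events.* Those recorded as AEs before version 6.0 are removed, and later ones need not have been reported. The AE tables keep only the serious events and the metformin-attributed GI events that stopped study drug.
- *The appendix does not include them.* Those recorded before version 6.0 stay in, while later ones need not have been reported. The tables mix two reporting regimes, and the percentages are too low because participants from the later period count in the denominator without full capture.

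Neither case gives a complete frequency by arm.

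**Step 2: how far the drug-cessation exception reaches.** It applies to item ii only. Nausea, vomiting and flatulence are in both items, so a non-serious event of these types that stops study drug is reportable if attributed to metformin and exempt if attributed to pregnancy. In a blinded trial that attribution is a judgement. Even the drug-stopping tier is therefore not certain to be complete in the AE tables.

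**Step 3: every SAP item that might report these events.**

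| SAP section | What it gives | Why it does not close the gap |
|---|---|---|
| 5.2.2 and 13.2, hypoglycaemia | Neonatal outcome | Not maternal |
| 5.2.2 item 14, "Glycemic control, measured by participant glucocometer" | Undefined glucose measure | No event definition or count; not carried into 13.2. Protocol 8.4.7 assigns the downloaded data to a future observational study |
| 13.2, maternal-morbidity proportion | By-arm model | Components undefined; the only maternal ones 13.2 names are hypertensive disorders and haemorrhage |
| 11.1, "Number of participants who completed the study medication" | Count by arm | All causes together |
| 12.3 | Baseline GI history | Not on treatment |
| 12.4 | Adherence per visit and overall, relative to maximum tolerated dose | No symptoms |
| 13.2, acceptability | Questionnaire outcomes | No event frequency |
| 14.1 | Total dose by arm and visit, plus "An exploratory analysis of how drug exposure may be related to changes in safety assessments will also be performed" | The safety assessments are not named |
| 14.3.1 | Withdrawals due to AEs by arm | Misses women who have symptoms and continue |
| 14.5 and 14.6 | Laboratory values and vital signs | Neither symptoms nor hypoglycaemic events |

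SAP 18 limits the tables to the analyses that the SAP describes, so none is implied elsewhere.

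**Step 4: the counting unit.** SAP 13.1 says 24 women entered more than once, giving 49 pregnancies, that is 49 − 24 = 25 repeat entries. If all are among the 535 of SAP 8.1, there are 535 − 25 = 510 different women. Any new table has to say whether it counts pregnancies or women.

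**The case against.** The best case for the plan is that tolerability is not ignored. Adherence, total dose, completion of medication, withdrawals due to AEs and acceptability are all planned, and dose-limiting intolerance would leave a trace in several of them. The maternal-morbidity proportion in SAP 13.2 is listed separately from morbidity at delivery, so it could be meant to hold the maternal events that protocol 10.2 calls study outcomes. SAP 4 also permits further analyses. In addition, the sentence in SAP 14.3.3 stands under a heading about AE assessments, so by itself it says little about events that are not AEs.

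Part of this stands. It would go too far to say that the outcome role is never fulfilled, because the undefined morbidity item leaves that open. What the documents show is that no section explicitly assigns these events to an analysis. The sentence in 14.3.3 has to be read together with 14.2, 15 and 18. The indirect measures, however, do not say how many women in each arm had symptoms, and a table added under SAP 4 would be labelled as unplanned.

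A reader might also infer three stronger things that the documents do not support:
- *That SAP 14.2 deliberately removes all GI and hypoglycaemia AEs.* Its wording follows the protocol's separate list of events common in pregnancy, and its appendix is not available to check.
- *That every GI event leading to a stop of study drug is safely captured.* The exception covers only those attributed to metformin.
- *That the hidden GI burden rivals the targeted benefit.* No GI or hypoglycaemia rate is given, so any such figure would only reflect the rate assumed.

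**Conclusion.** The omission is real and should be corrected before the safety analysis is run. Non-serious maternal GI symptoms and maternal hypoglycaemia without admission are exempted from AE reporting as CRF outcomes and reviewed throughout treatment, but they are not explicitly assigned to any post-baseline summary by arm. Followed as written, the safety tables would under-report the effects the protocol expects, and the tolerability conclusion would be incomplete. This holds whichever lists the SAP 14.2 exclusion covers.

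The size cannot be given, since the documents contain no event rate from which to derive it. The conclusion assumes that the appendix contains only a list of exempted events, as SAP 14.2 describes it, and no analysis. The primary analysis is unaffected.

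**What to change.** 1. In SAP 14.2, state which of the protocol 10.2 lists the exclusion covers. The exclusion itself can stay.
2. Add to SAP 14, for the safety set by arm, from the visit-level CRF data and across the periods before and after version 6.0, the number and percentage of randomised pregnancies with:
   - at least one on-treatment GI symptom, by type where the CRF records it, shown alongside baseline GI status;
   - at least one maternal hypoglycaemic event.

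   A risk difference with a 95% CI is preferable for each; plain counts and percentages would close the basic gap. Say how repeat entries are counted.
3. Tabulate discontinuation of study drug for GI reasons by arm, where the reason recorded under protocol 8.8 or the AE form's entry on study-drug action (protocol 10.3.1) identifies it.
4. Amend SAP 14.3.3 and 15 to match.

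The cost is SAP wording and a few extra tables built on reviews that the protocol already schedules. The CRF was not supplied, so the breakdown by symptom type and the discontinuation table depend on which fields it holds.

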14.4 Pregnancies

Not applicable.

14.5 Clinical Laboratory Evaluations

Lab tests will be completed at the randomisation visit, 32 gestational weeks (+/- 1 week) AND at 38 gestational weeks (+/- 1 week), and 12 weeks post-partum (+/- 4 weeks).

The following laboratory assessments will be analysed locally:

At randomisation: HbA1c, fasting glucose, Insulin, c-peptide, total cholesterol, High-Density Lipoprotein (HDL) cholesterol, Low-Density Lipoprotein (LDL) cholesterol, triglycerides (Tg), urea, creatinine, alanine aminotransferase (ALT), and aspartate transaminase (AST).

At 32 weeks gestation: HbA1c, fasting glucose, total cholesterol, HDL cholesterol, LDL cholesterol, Tg, urea, creatinine, ALT, and AST.

EMERGE NUIG-2016-01, Statistical Analysis Plan Version 1, 21/03/2023

At 38 weeks gestation: HbA1c, fasting glucose, total cholesterol, HDL cholesterol, LDL cholesterol, Tg, urea, creatinine, ALT, and AST.

At 12 weeks post-partum: fasting glucose, 2h glucose, fasting insulin, fasting c-peptide, HbA1c, total cholesterol, HDL cholesterol, LDL cholesterol, Tg.

Descriptive summaries (mean, SD, median, minimum, and maximum) of changes from baseline will be presented for clinical laboratory values by treatment group and visit for the Safety Population.

The number of participants (counts and percentages) with clinically significant laboratory abnormalities at each visit will be highlighted for each lab test, for the Safety Population by treatment group.

14.6 Haemodynamics (Vital Signs)

The analysis of Vital signs will include the measurements specified in the corresponding CRF form. These measurements are the heart rate, blood pressure, weight, height and BMI. For each of these measurements, the analysis will include:

- Summaries of the results by visit (mean, SD, median, min and max) and by treatment arm.
- Summaries of the absolute changes from baseline by visit (mean, SD, median, min and max) and by treatment arm.

14.7 ECGs

Not applicable.

15 Other Planned Analysis

No other analyses planned.

16 Reporting conventions

P-values ≥ 0.001 will be reported to 3 decimal places; p-values less than 0.001 will be reported as " <0.001 ". The mean, standard deviation, and any other statistics other than quantiles, will be reported to one decimal place greater than the original data. Quantiles, such as the median, or minimum and maximum will use the same number of decimal places as the original data. Estimated parameters, not on the same scale as raw observations (e.g., regression coefficients) will be reported to 3 significant figures.

17 **References**

- WHO. Diagnostic criteria and classification of hyperglycaemia first detected in pregnancy: a World Health Organization guideline. *Diabetes Res Clin Pract* 2014;103:341-63.
- ADA. American Diabetes Association Position statement: Gestational Diabetes Mellitus. *Diabetes Care*. 2004;27(Suppl 1):S88-S90.
- O Sullivan EP, Avalos G, O Reilly M, Dennedy C, Dunne F. ATLANTIC DIP: The prevalence and outcomes of gestational diabetes mellitus using new diagnostic criteria. *Diabetologia* 2011; 54(7):1670- 1675.

18 ***Listing of Tables, Listings and Figures***

Tables, listings and figures will be used to summarise the results of the analyses described in this SAP. Tables, listings and figures in the CSR will clearly display the title, endpoint(s) population, summary statistics calculated, type of analysis used, time points and any relevant footnotes.
